Aim 1 tests whether the Mindful Living vs. HL intervention increases HRQOL, and decreases in perceived stress (primary), and decreases anxiety, depressive mood, and fatigue (secondary) during a 11-week intervention, and whether changes are sustained over a 12-month follow-up. Based on preliminary data, there will be a detectable differences in mean immediate (post-treatment) change from baseline and in mean sustained change (6 and 12 month) from baseline, for the primary and secondary outcome measures between the ML and the HL arms with an anticipated final sample size of 192 subjects. The detectable group mean difference was calculated for a two-tailed test at the 0.05 significance level with 0.80 power for a final sample

size of 96 subjects per treatment arm for a cluster-randomized design with corresponding intracluster correlation coefficient (ICC) estimated from our pilot data. The 96 subjects are from 16 web-groups (cohorts) per arm with an average of 6 subjects per cohort. This assumes 25% dropout, so that a total of 256 subjects will be enrolled, comprised of 32 cohorts, with 8 subjects per cohort, that will be randomized to one of the two treatment arms. Based on the calculations below we anticipate that our sample size and the variability in our data will enable us to detect smaller intervention effects than those observed in our pilot for our primary variables and for several of our secondary variables for Aims 1 and 2. The effect sizes we anticipate being able to detect are consistent with the medium effect sizes generally observed in other studies of psychosocial interventions in cancer survivors.

	SD		Detectable difference (effect size=diff/pooled SD)			Between Group Difference in Immediate Change (from pilot)	
Outcome Variables Aim 1	Between Subject	Residual	ICC	Immediate (Post-tx)	Sustained (6 and 12 mo.)	Observed Mean (effect size)	95% CI
FACT-Total	13.6	9.3	0.010	5.5 (0.19)	6.1 (0.46)	9.1 (0.69)	(-3.7, 22.0)
PSS	7.1	4.2	0.010	2.5 (0.29)	2.8 (0.47)	-6.7 (-1.13)	(-12.6, - 0.9)
CESD	7.6	5.3	0.150	4.1 (0.34)	4.5 (0.60)	-5.8 (-0.77)	(-13.0, 1.5)
POMS-anxiety	4.1	2.9	0.078	2.0 (0.49)	2.2 (0.54)	-2.0 (-0.49)	(-6.0, 1.9)
POMS-fatigue	4.6	2.9	0.204	2.4 (0.59)	2.7 (0.66)	-2.0 (-0.49)	(-5.9, 1.9)
AIM 2							
MOCS relaxation	1.4	1.2	0.125	0.9 (0.53)	1.0 (0.59)	3.0 (1.77)	(1.0, 5.0)
MOCS coping	4.1	1.8	0.010	1.1 (0.43)	1.2 (0.47)	3.8 (1.49)	(0.7, 6.9)
FMI	7.4	3.5	0.010	2.1 (0.42)	2.3 (0.46)	3.5 (0.71)	(-1.7, 8.8)

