The statistical analyses for Aim 2 will examine potential mediators of any observed intervention effects on outcome measures, with examination of skills that support post-intervention and sustained skills. For Hypothesis 2A effects of the intervention on relaxation, coping, mindfulness and acceptance outcomes, the analytic plan will be similar to those in Aim 1, with similar targeted effect sizes and similar power projections. For Hypothesis 2b, testing mediation of intervention effects, mediation analysis will explore the causal pathway between intervention (ML and HL) and changes in primary outcomes (HRQOL, depressed mood, and perceived stress) and secondary outcomes (anxiety and fatigue) from baseline to post-intervention (immediate) and from baseline to 12 months (sustained) with change in reported relaxation, mindfulness, acceptance, and cognitive coping skills as mediators. With the independent variable X (intervention) randomized to web-group cohorts, and the mediator variables M (change in mastery in relaxation, mindfulness, avoidance, and cognitive coping skills), and the dependent variable Y (change in HRQOL, depressive mood, stress, and secondary variables) measured at the subject level within cohorts, we have a two-level hierarchy with a 2-1-1 design. For this multilevel design, multilevel structural equation modeling (MSEM) will be used to estimate and test the direct and indirect effects to assess multilevel mediation⁵⁷ using SEM or GSEM in Stata or MPLUS.

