Power for Hypothesis 2B is based on the pilot data where large effects of group assignment (ML vs. HL) were observed on changes in potential mediators (relaxation, coping skills, mindfulness, and acceptance; range of d = .70-1.7). In the proposed model multilevel mediation framework this effect will include some variance attributable to the cohort to which the subject is randomized within the treatment arm, as well as the effect of the treatment itself, the latter of which is the effect of interest. We therefore conservatively estimate the true treatment effect for the mediators to be d = .60, representing the first arm of the mediation pathway. The second arm of the mediation pathway reflects the association between change in the mediators (relaxation, coping, mindfulness, and acceptance) and change in the outcomes of interest (HRQOL, stress, etc.) In our pilot work shown above, the absolute correlation values between these change variables ranged from .41-.76, corresponding to a d range of .89-2.3,58 and we conservatively adopt this lower estimate (.89) for purposes of estimating power. Here we use the Monte Carlo approach for evaluating indirect (mediation) effects with 5000 replications and two Monte Carlo draws per repetition and an attrition-adjusted sample size of 192 (96 per group).⁵⁹ This produces power in excess of .99 for calculating significant mediated effects with a 95% confidence interval. In the event that the true effect sizes are substantially smaller (i.e., d=0.4 rather than .6 for the first path, and d = .6 rather than .89 for the second path) we will still have .80 power to detect significant mediated (indirect) effects.

7.3. Statistical Analyses for Aim 3

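### Mediation power in Section 7.2 leaves out the clustering that Table 6 allows for, and three effect sizes in Table 6 do not fit the table's own figures

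*Combined protocol and SAP*

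**What the plan says.** Section 7 and Table 6 give detectable differences "calculated for a two-tailed test at the 0.05 significance level with 0.80 power", adjusted for clustering. The basis is: "The 96 subjects are from 16 web-groups (cohorts) per arm with an average of 6 subjects per cohort". Each row has an ICC and a raw detectable difference, with a bracketed effect size that the header defines as the difference over a pooled SD.

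- For the four mediators, the immediate effects detectable at 0.80 power are 0.42 (FMI, ICC 0.010), 0.43 (MOCS coping, 0.010), 0.53 (MOCS relaxation, 0.125) and 0.65 (AAQ, 0.284).
- For the three primary outcomes, the immediate entries are 5.5 (0.19) for FACT, 2.5 (0.29) for PSS and 4.1 (0.34) for CES-D. The text calls the detectable effects "consistent with the medium effect sizes generally observed in other studies".

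Section 7.2 recognises the clustering for the analysis: "we have a two-level hierarchy with a 2-1-1 design". It plans the intervention's effect on the skills (Hypothesis 2a) "with similar targeted effect sizes and similar power projections" to those of Aim 1. For mediation (Hypothesis 2b) it assumes d = .60 for the first path and d = .89 for the second, with "two Monte Carlo draws per repetition and an attrition-adjusted sample size of 192 (96 per group". It states: "This produces power in excess of .99 for calculating significant mediated effects with a 95% confidence interval". If the paths are only .4 and .6, it states that "we will still have .80 power to detect significant mediated (indirect) effects". Neither an ICC nor a number of cohorts appears in this calculation.

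**The concern.** The first mediation path is the same comparison that Table 6 covers: arm against change in the skill, with 96 per arm in cohorts. The d scale is also the same, because the pilot range of .70 to 1.7 in Section 7.2 matches the observed mediator effects of 0.71 to 1.77 in Table 6. To declare mediation with a valid interval, the first path must in effect be distinguishable from zero, so its power is a practical ceiling. Table 6 needs 0.65 for 0.80 power on AAQ, so .99 at .60 cannot hold there. All four mediators need more than .40 for 0.80 power, so the fallback claim cannot hold for any of them.

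This is the only power justification for Hypothesis 2b, which belongs to a specific aim and not an exploratory one. A null mediation result for acceptance or relaxation could be read as strong evidence against mediation when the power was well below the stated figure. In Table 6, a reader would think the trial powered for standardised primary effects of 0.19 to 0.34.

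**Working it through.** **Inputs.** Section 7 and Table 6: 96 per arm, 16 cohorts of 6 per arm, two-sided 0.05, mediator ICCs 0.010, 0.125 and 0.284. Section 7.2: first path d = .60 (fallback .40), second path d = .89 (fallback .60), N = 192.

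**The plan's figures without clustering.** The first path has noncentrality d × √(96/2) = d × 6.928. At .60 this is 4.157, and power is Φ(4.157 − 1.96) = .986. At .40 it is 2.771, and power is .79. The second path converts by r = d/√(d² + 4), giving r = .407 for .89 and .287 for .60. Simulating the indirect effect with N = 192, 5,000 trials and 2,000 draws per interval gives .984 and .768. The printed figures are thus nearly reached, but only with clustering ignored.

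**Table 6's own method.** With design effect 1 + 5 × ICC, the detectable d is (t.975 + t.80) × √(2/96 × design effect) on 30 df. This gives 0.428, 0.533 and 0.650 for ICCs 0.010, 0.125 and 0.284, which agrees with the table.

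**First-path power with Table 6's ICCs.** The noncentrality is d × √(48/(1 + 5 × ICC)). Ranges run from t on 30 df to the normal approximation.

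| Mediator | Design effect | Effective N | Power at d = .60 | Power at d = .40 | d needed for .99 |
|---|---|---|---|---|---|
| FMI, MOCS coping | 1.05 | 183 | .975–.98 | .74–.77 | 0.63–0.66 |
| MOCS relaxation | 1.625 | 118 | .88–.90 | .56–.59 | 0.79–0.82 |
| AAQ | 2.42 | 79 | .73–.76 | .41–.43 | 0.96–1.00 |

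For example, AAQ at .60: .60 × √(48/2.42) = 2.672, and Φ(2.672 − 1.96) = .76.

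These are upper limits. If the second path is taken between cohorts, power falls further. A cohort-mean simulation (32 cohorts of 6), with the outcome's residual ICC **assumed** at 0.010 to 0.204 (the range of Table 6's Aim 1 outcomes), gives .41–.73 at d = .60 and .16–.28 at d = .40.

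**Number of draws.** Two draws cannot form a 95% interval. Taken literally, two draws give .997 and .96, but 67–68% of trials with no first-path effect are then declared mediated. With 2,000 draws that rate is 5.3%.

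**Effect sizes in Table 6.** Nine rows with three bracketed values each make 27. Difference/(residual SD × √2) reproduces 24 of them to rounding. The exceptions are the three immediate primary entries:

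- FACT: 5.5/(9.3 × 1.414) = 0.42, printed 0.19
- PSS: 2.5/(4.2 × 1.414) = 0.42, printed 0.29
- CES-D: 4.1/(5.3 × 1.414) = 0.55, printed 0.34

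The sustained and pilot values in the same rows do fit, for example 6.1/13.15 = 0.46 for FACT. The between-subject, residual and total SDs do not reproduce the three printed values. The raw differences do reproduce (normal to t on 30 df): 5.45–5.63, 2.46–2.54 and 4.01–4.14.

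**The case against.** The strongest reply is that Section 7.2 does mention cohort variance and lowers the pilot range to .60 because of it. Dividing the pilot effects by the square root of the design effect gives .69 (FMI), 1.39 (relaxation), 1.45 (coping) and .49 (AAQ), so .60 could be read as a conservative, cohort-discounted effect for three of the four mediators. That reading is fair to relaxation if its true effect is near the pilot's. However, the section calls .60 the true treatment effect, and a smaller mean difference does not widen the standard error. The reading also fails for AAQ: even at its full pilot effect of 0.76, first-path power is Φ(0.76 × 4.454 − 1.96) = .92. Nor does it rescue the fallback, because d = .40 with no clustering at all gives .79 on the first path alone.

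Other points stand in part:

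- The two draws are probably a wording slip. Two draws would have given about .96 in the fallback, not .80. The wording still needs correcting, and the conflict over clustering does not depend on it.
- The unclustered shortfalls are small and would not justify a comment alone.
- The between-cohort figures rest on an assumed ICC and an approximation. They also order the mediators differently, with FMI and coping lowest at d = .60. They show only that the ceilings may be generous.
- The documents do not say whether another SD was intended for the three bracketed entries. Their implied SDs (28.9, 8.6 and 12.1) match none in the table.
- The planned analysis is already multilevel, so inference for Aim 2 is unaffected.

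**Conclusion.** The concern holds. On the plan's own ICCs and cohort numbers, the .80 fallback claim fails for every mediator, by about 3 to 6 points for FMI and coping and by nearly 40 for AAQ. The claim of more than .99 is impossible for AAQ (at most .76), materially too high for relaxation (at most .90) and slightly high for FMI and coping (at most .98). This rests on equal cohorts of 6, on Table 6's pilot ICCs, and on the first path as a practical ceiling for the indirect effect.

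Separately, 0.19, 0.29 and 0.34 in Table 6 are inconsistent with the divisor used in the rest of the table, which gives 0.42, 0.42 and 0.55. These values also fit the description of medium effects. The raw detectable differences, the sample size and the planned analyses are not affected. The point should be corrected because readers will rely on these figures to interpret the results.

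**What to change.** - In Table 6, replace 0.19, 0.29 and 0.34 with 0.42, 0.42 and 0.55, and keep the raw differences.
- In Section 7.2, withdraw both power claims. Rerun the mediation simulation with 16 cohorts of 6 per arm, Table 6's ICCs, the planned multilevel model and a stated number of draws large enough for a 95% interval.
- State the assumed outcome ICC and whether the second path is within or between cohorts, and report power per mediator.
- If the first-path figures tabulated above are quoted, label them as upper limits. Note that a between-cohort second path gives lower values that depend on the assumed outcome ICC.

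The cost is three table entries, two sentences and one simulation. No patients are added, and neither the analysis nor the conduct of the trial changes. The stated mediation power will look less favourable.

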7.4. Missing Data

While every effort will be made to follow-up with subjects, it is expected that approximately 25% of the subjects may be lost at follow-up. Reasons for subject drop-out will be recorded and compared between treatment groups. Participant characteristics and outcome measures collected prior to drop-out will be compared between those that drop out and those that complete the study. In the presence of missing data, under the assumption of missing at random (MAR), linear mixed model analysis which can handle incompletely observed subjects and uses a likelihood estimation method will provide correct likelihoods and lead to valid estimates. However, since the data under analysis cannot distinguish if data is MAR or it is missing not at random (MNAR), sensitivity analysis will also be performed following approaches recommended by Molenberghs and Kenward.⁶⁰ Methods for sensitivity analysis such as marginal delta adjustment, conditional delta adjustment, reference-based controlled imputation, and pattern mixture models will be considered. Nonnormality will be assessed, and if needed, variables will be transformed to approximate normality before imputation and retransformed back to original scale values. To avoid imputation bias, all variables in the substantive analyses and, if feasible, all variables predictive of the missing values (i.e. immediate post and 6 month response of the outcome measure, if available) or variables influencing the cause of missing data will be included. These multiple imputation analyses will be conducted using SAS PROC MI and SAS PROC MIANALYZE.

8. Data Collection and Record Keeping

The study will be administered by the lead institution, University of Iowa (UI). It will be monitored by a single Institutional Review Board at UI, which will set up reliance agreements with the Fred Hutch/University of Washington Cancer Consortium and UM IRBs. Each of the sites will be responsible for the screening, recruitment, enrollment, and support of assessment completion of subjects recruited at their respective institutions. The Coordinating and Data Core at UI will develop standardized operating procedures for regulatory and protocol compliance for all 3 clinical sites (UM, Fred Hutch/University of Washington Cancer Consortium, and UI) and for all study activities and data collection.

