6.5. Risks

Based on our previous work, this study as described is of minimal risk. Minimal risk is defined as the probability and magnitude of harm or discomfort anticipated in the research not greater than that ordinarily encountered in daily life or during routine physical or psychological exam.

During the psychosocial questionnaire administration, there are minimal potential emotional risks to subjects due to the somewhat personal nature of the questions asked regarding mood and quality of life. Answering the questions may make subjects upset or uncomfortable; subjects will be informed that they can choose not to answer questions they do not wish to answer.

During the group conferencing sessions, sensitive topics may be discussed; subjects are free to participate as much or as little as they feel comfortable.

There is a potential loss of confidentiality from the web conferencing format; all subjects will be instructed in confidentiality practices at the beginning of the groups (see below).

Risks of Immune Response Sub-Study

Slight discomfort or stinging sensation when using the lancet. Small risk of infection and/or bruising.

What Is Done To Minimize The Risks

Because interactions will be in a group setting, in the first session subjects will be instructed about the importance of confidentiality. They will be required to access the web-based intervention in a private location where others could not overhear the group conversation. Additionally, subjects can choose to disclose as much or as little personal information as they feel comfortable with in the group. Confidentiality of subject information will be strictly preserved, and subject names will not be revealed in publications or reports.

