Descriptive statistics will be computed for all demographic and baseline variables for each of the treatment arms and distributions of continuous variables will be evaluated for normality. If data are non-normal, appropriate transformation will be applied or non-parametric methods may be used. Demographic and baseline variables will be compared between treatment groups using ttest for continuous variables, Wilcoxon-rank sum test for ordinal, and non-normally distributed continuous variables, and Pearson Chi-square test for categorical variables. Variables found to differ significantly between the groups will be used as covariates in the comparison of outcome measures between the treatment groups. A number of variables known to influence our primary outcomes (e.g., income, education, marital status, and race/ethnicity) will be considered as possible covariates. These putative control measures will be analyzed as covariates if they are correlated with our outcomes (at p<.10). The internal consistency (coefficient alpha) and testretest correlations over the course of data collection will be evaluated for multi-item inventories. While every effort will be made to follow-up with subjects, it is expected that approximately 25% of the subjects may be lost across the study period. Intent to Treat (ITT) analysis will be performed using all available data for all randomized subjects. Reasons for subject drop-out will be recorded and compared between treatment groups. Subject characteristics and outcome measures collected prior to drop-out will be compared to those that complete the study follow-up. In the presence of missing data, under the assumption of missing at random (MAR), linear mixed model analysis, which can handle incompletely observed subjects and uses a likelihood estimation method, will provide correct likelihoods and lead to valid estimates. However, since the data under analysis cannot distinguish if data is MAR or if it is missing not at random (MNAR), sensitivity analysis will also be performed using pattern mixture models. Multiple imputation will be used for sensitivity analysis by imputing from a non-random pattern mixture model. Per protocol analyses will be performed including participants that attended at least 6 sessions of their respective intervention condition and completed the immediate post-intervention surveys or any subsequent follow-up surveys.

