AAQ	2.8	2.5	0.284	2.3 (0.65)	2.5 (0.71)	-2.7 (-0.76)	(-6.3, 1.0)

Table 6. Power Considerations

7.1. Statistical analyses for Aim 1

Aim 1 will be tested using linear mixed model (LMM) analyses for repeated measures with treatment group (ML vs. HL), time, and treatment*time interaction as fixed effects. Random effects include web group cohort (within treatment) and subjects (within cohort, within treatment). In fitting the LMM, appropriate covariance structures for the longitudinal measures within subject will be considered, such as compound symmetry, or heterogeneous compound symmetry, and then selected based on Akaike Information Criteria (AIC) and Schwarz's Bayesian Information Criteria (BIC). Specifically, to test for immediate change (post-intervention), the linear mixed model analysis will include the baseline and immediate post-intervention timepoints. The difference in immediate change post-treatment between the different conditions will be tested by the interaction effect. For the mixed model analysis of long-term change, data from all 4 timepoints will be used in fitting the model, with the difference in long-term change at 6 and 12 months assessed using tests of mean contrast. Bonferroni adjustment will be applied to the p-value to test for long-term change at 6 and 12 months. For each of the two analyses, if confounding variables are found to differ between the treatment groups such that covariate adjustment is necessary, a secondary comparison of the primary outcome variable between treatment groups will be made by expanding the LMM to include covariates. These variables may include age, education, income, race/ethnicity, geographic location, recurrence, maintenance chemotherapy, recurrence during the study period, and disease stage. Statistical significance for efficacy of ML vs. HL will be based on a two-tailed test at the 0.05 significance level with treatment effect summarized as mean difference with 95% confidence interval. Similar analyses will be performed for the secondary outcome measures.

7.2. Statistical analyses for Aim 2

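### The 12-month mediation analysis (Hypothesis 2b) is fitted to change scores without the post and 6-month scores, so the mixed-model missing-data argument does not cover it and its direct and total effects can be biased

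*Combined protocol and SAP*

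**What the plan says.** Section 7 (opening) and Section 7.4 give the same missing-data argument. Under missing at random, "linear mixed model analysis which can handle incompletely observed subjects and uses a likelihood estimation method will provide correct likelihoods" and hence valid estimates. Section 7.4 adds that "it is expected that approximately 25% of the subjects may be lost at follow-up". Section 7 also promises that "Intent to Treat (ITT) analysis will be performed using all available data for all randomized subjects".

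Section 7.1 fits the Aim 1 mixed model to all four assessments when it tests long-term change. Section 7.2 uses a similar plan for Hypothesis 2a (effects on skills). For Hypothesis 2b (mediation) it changes method: a multilevel structural equation model (MSEM) on subject-level changes, from baseline to post-intervention and "from baseline to 12 months (sustained) with change in reported relaxation, mindfulness, acceptance, and cognitive coping skills as mediators". It will estimate and test both direct and indirect effects, in Stata or Mplus. It names no rule for missing data, gives the 12-month model no post or 6-month scores, and does not say at which visit the mediator change ends.

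Section 7.4 describes multiple imputation that may use the earlier outcome responses. It does so as a sensitivity analysis, with methods to be considered, and does not tie it to Aim 2. Table 3 schedules mediators and outcomes in the same assessment battery.

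**The concern.** A mixed model of repeated scores is protected under missing at random because a woman who leaves after the post or 6-month survey still contributes those scores, and they carry the information about why she left. A change score from baseline to 12 months discards them. Without the 12-month survey her outcome change does not exist. If the mediator change is also taken at 12 months, neither variable exists, and likelihood estimation on arm and two change scores learns nothing from her.

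Two analyses of the same 12-month effect would then rest on different assumptions. Aim 1 is valid if loss depends on observed interim scores. Hypothesis 2b needs something close to loss that does not depend on them differently by arm. The quantity most exposed is the direct effect, which Section 7.2 plans to test. A spurious one would be read as Mindful Living working partly outside the skills it teaches. Arm-specific loss is conceivable: the arms differ in content and facilitators (Section 6.4), and the plan itself intends to compare drop-out reasons between arms.

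**Working it through.** **1. The plan's own figures.** Section 7 states that "a total of 256 subjects will be enrolled, comprised of 32 cohorts" of 8. With 25% loss, 256 × 0.75 = 192 and 256 − 192 = 64. The 192 is reproduced exactly. For mediation power at n = 192, convert d to r by r = d/√(d² + 4): 0.60 gives 0.287, 0.89 gives 0.407, 0.40 gives 0.196. A single-level Monte Carlo check that ignores clustering gives power of .98 to .99 in the base case (plan: above .99) and .72 to .78 in the pessimistic case (plan: .80). These are close enough to use the plan's inputs.

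**2. Who contributes to the 12-month fit.**

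| Last survey completed | Section 7.1 mixed model | Section 7.2, 12-month changes |
|---|---|---|
| Baseline only | baseline score | nothing |
| Post | baseline, post | no outcome change; mediator change only if it ends at post |
| 6 months | baseline, post, 6 months | as above |
| 12 months | all | both changes |

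**3. Simulation under full mediation.** Inputs from the documents: Table 6 residual SDs (FACT 9.3, FMI 3.5) and between-subject SDs (13.6, 7.4); path a d = 0.60 and change correlation 0.41 (Section 7.2); 256 women; 25% loss.
- FACT change SD = √2 × 9.3 = 13.15. As a cross-check, Table 6's sustained 6.1 at effect size 0.46 implies 6.1/0.46 = 13.3.
- True total = 0.60 × 0.41 × 13.15 = 3.2 points, all indirect; true direct = 0.

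Assumed, not in the documents: 10% lost at random after baseline; the rest lost after the post survey, with log-odds of 0.7 to 1.2 per SD of poorer observed FACT change in the ML arm and random loss in HL. Cohort correlation is ignored (Table 6 gives 0.010 for both measures).

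| Analysis | Total | Direct | False-positive rate, direct | Share mediated |
|---|---|---|---|---|
| Truth | 3.2 | 0 | 5% | 100% |
| 12-month changes, completers | 3.9 to 4.3 | 0.5 to 1.0 | 5-9% | 78-87% |
| All visits, likelihood | 3.1 to 3.2 | −0.1 to 0.0 | – | – |

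Relative error in the total: 3.9/3.2 = 1.22 and 4.3/3.2 = 1.34, so roughly 20-35%. If HL loss runs in the opposite direction, the total reaches 4.6 and the false-positive rate 11%. The indirect effect moves about 3-6%.

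**4. Second simulation, partial mediation.** Truth: total 6.1, direct 2.8, indirect 3.3. Large sample, no clustering, 25% loss of the 12-month visit, log-odds 0.5 to 1.0 per SD of poorer interim outcome.

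| Loss mechanism | Total | Direct | Indirect |
|---|---|---|---|
| Random, or differing only by arm | 6.1 | 2.8 | 3.3 |
| Same slope in both arms | 5.9 to 5.5 | 2.7 to 2.5 | 3.2 to 2.95 |
| HL only | 4.8 to 3.4 | 1.7 to 0.75 | 3.0 to 2.7 |
| ML only | 7.4 to 8.4 | 3.9 to 4.7 | 3.5 to 3.6 |
| Each of these, post and 6-month scores of both variables used | 6.1 to 6.15 | 2.7 to 2.8 | 3.3 |

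Here the indirect effect moves more than in step 3, at worst from 3.3 to 2.7 (HL only, slope 1.0). The common-slope error in the total is at most 0.6 of 6.1, about 10%.

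**5. If the mediator change ends at post-intervention** and everyone has it, likelihood estimation without interim outcomes still gives direct effects from 0.76 to 4.74 (truth 2.8) and totals from 3.95 to 7.94 (truth 6.1). The indirect effect stays at 3.1 to 3.3.

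**The case against.** The strongest reply is that nothing in the plan restricts the mediation to completers. Section 7 promises intention-to-treat on all available data, Section 7.4 describes imputation that draws on earlier responses, and the Section 7.4 sentence speaks only of the mixed model, for which it is right. On this view the plan is merely silent on one estimator. The first part stands: completers-only is the practical effect of the variables chosen, not a stated rule. The conclusion does not follow. The specified 12-month variables leave the interim scores out, and imputation is offered only as a sensitivity analysis.

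Several stronger readings are tempting and should be set aside.
- A reader might infer that the 192 in the mediation power paragraph proves a completers-only set. It does not: Section 7 uses the same 192 for Aim 1, which is analysed on all visits.
- A reader might infer that no likelihood method could use the earlier answers. Full-information likelihood can, if they enter as auxiliary variables; the plan just does not add them.
- A reader might infer that all of Aim 2 is affected. Hypothesis 2a follows the Aim 1 model and is covered.
- A reader might infer that both changes come from the 12-month survey. Section 7.2 does not say.
- A reader might extend the point to women with missing covariates. The documents give no missing rate, the freedom to skip questions in Section 6.5 is described for mood and quality-of-life items, and covariate adjustment is a conditional secondary comparison.

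It is also fair that the loss slopes are assumed, that the false-positive range starts at the nominal 5%, and that Section 7.2 powers only the indirect effect, which is the more robust quantity.

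**Conclusion.** The concern holds for Hypothesis 2b at 12 months. The missing-at-random justification does not carry over from the mixed model to an MSEM on change scores, and the 12-month fit is in effect close to completers-only unless earlier scores are added. With 25% loss that depends on interim outcome differently by arm (log-odds 0.7-1.2 per SD, assumed), the total effect is off by roughly 20-35%, and a direct effect of about 0.5-1.0 FACT points appears where there is none. Both errors are larger if the arms run in opposite directions. The indirect effect shifts about 3-6% in that set-up, and more in the partial-mediation set-up. With random loss the bias is near zero; with the same mechanism in both arms it is near zero in the first set-up and modest in the second. The documents do not say which pattern will occur. The baseline-to-post mediation has the same gap in milder form. This should be corrected, but it does not threaten the Aim 1 result.

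**What to change.** Amend Section 7.2 so that the main 12-month mediation uses the baseline, post and 6-month scores of both mediator and outcome, in one of two ways:
- multiply impute the visit scores, separately by arm and respecting cohort, then form the changes and fit the MSEM to each completed data set; or
- fit the MSEM by full-information likelihood with the earlier scores as auxiliary variables.

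State the visit at which the mediator change ends. Say in Section 7.4 that the mixed-model argument covers Aim 1 and Hypothesis 2a, and that Hypothesis 2b relies on the method above under the same missing-at-random assumption. The delta-adjusted and pattern-mixture analyses can remain as sensitivity analyses.

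The cost is SAP text, more programming and a somewhat larger model. If Section 7.4's SAS imputation is used, the completed data sets must be passed to Stata or Mplus. A full four-wave MSEM is not required, and with 32 cohorts it may be hard to fit. No new data are needed.
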